Cover page

Official Title: LSA Reconstruction With Laser Fenestration During the TEVAR

NCT number: NCT03845829

Date of the document: November 1, 2020

- **Study Protocol**
- **Objective** This study aimed to prospectively evaluate the safety and efficacy of left subclavian artery (LSA) revascularization via in-situ laser-assisted fenestration during thoracic endovascular aortic repair (TEVAR) for type B aortic dissection (TBAD).
- **Design** This was a prospective, single-arm, multicenter study that enrolled patients with complicated or high-risk acute TBAD. The LLTEVAR (LSA Revascularization With Laser-assisted Fenestration During TEVAR) study is a prospective, single-arm, multicenter trial that planned to enroll 100 patients at 5 vascular centers (NCT03845829). Patients presenting with complicated or high-risk acute TBAD with a proximal entry tear originating in zone 2 or zone 3, who were deemed appropriate candidates for TEVAR in conjunction with LSA revascularization, met the included criteria, and consented to participate were enrolled. The distance from the proximal edge of LSA orifice to the intended proximal landing location should be >5 mm. Patients were excluded if they were pre-procedurally scheduled to have proximal aortic arch coverage in zone 1 or zone 0. Other main exclusion criteria included patients who were inappropriate for TEVAR due to unfavorable anatomic characteristics (no commercially available aortic stent for the size of the aorta, no available access for TEVAR, both LAS and left vertebral artery originated from aorta, et al), previous open surgery for aortic arch and connective tissue disorders. The primary safety endpoint was freedom from composite major adverse events (mortality, stroke, myocardial infarction, rupture, paraplegia, type Ia endoleak) within 30 days after the procedure. Univariate and multivariate analyses determined the risk factors of composite major adverse events. The primary efficacy endpoint was freedom from all-cause death, LSA in-stent restenosis, and reintervention due to dissection progression, growth, and endoleak at 1 year after the procedure.
- **Methods** Once diagnosed, all patients received optimal medical therapy, consisting of close intensive care unit monitoring and control of blood pressure, heart rate, and pain. TEVAR procedures were performed for patients with complicated and high risk TBAD. Patients not responding to medical therapy or presenting with rupture or impending rupture, malperfusion were treated emergently; otherwise, TEVAR procedures were performed 2 weeks later. The procedure of TEVAR in adjunct with in-situ laser-assisted fenestration for LSA revascularization has been previously described in detail [19-21]. Briefly, the TEVAR procedures were performed under local or general anesthesia, and aortic stent-grafts were deployed through femoral access, and the LSA fenestration stents were inserted through brachial artery. The diameter of the aortic stent-graft was based on the diameter of the proximal healthy landing zone of the aorta with approximately 5% oversizing. If the diameter of the stent-graft mismatched the diameter of the distal attachment site of the aorta (e.g, > 20% oversizing of the total aortic diameter), a distal restricted stent technique was used [24]. After aortic stent-graft deployed, a 6F steerable sheath combined with a balloon catheter (Mustang, Boston Scientific, 4mm in diameter and 4cm in length) allowed the laser tip to be placed in the intended fenestration site outside of the aortic stent-graft. After the

fenestration was established, the balloon catheter was pushed forward and through the fenestration hole, and after the balloon angioplasty for the established hole, the laser tip was exchanged with a 0.035-inch guidewire. Then the fenestration hole was subsequently dilated up to the reference diameter of the subclavian artery, and a balloon-expandable (Lifestream, BD) or self-expandable (Fluency, BD) covered-stent (10% oversizing of the LSA in diameter) was deployed inside the fenestration. Post stent dilation was always required for the LSA stent. At the end of the procedure, arteriography was performed from the ascending aorta to assess the success of the procedure and to identify potential endoleak and residual stenosis of the LSA stent.

- **Statistical Analysis Plan (SAP):** Continuous variables are presented as mean with standard deviation, and categorical variables are summarized using counts and proportion. Univariate logistics regression analysis was performed to determine the potential risk factors of major adverse events (mortality, stroke, myocardial infarction, rupture, paraplegia, type Ia endoleak, major bleeding, acute kidney injury, limb ischemia, bowel ischemia, retrograde dissection, stent-induced new entry (SINE), access site complications and unplanned reinterventions), and only factors being found statistically significant in the univariate analysis were included in the multivariate analysis. The patency rate of LSA and the all cause related mortality were estimated using the Kaplan-Meier method. SPSS version 26.0 (SPSS, Inc., Chicago, IL, USA) was used for the statistical analyses. Differences with a P value < 0.05 were considered statistically significant.
- **Informed Consent Form (ICF):** attachment
-

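### The 1-year efficacy composite is only weakly specific to LSA revascularization and, as worded, scores a failed or unstented fenestration as a success

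*Combined protocol and SAP*

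**What the plan says.** The Objective section of the Study Protocol sets out to "prospectively evaluate the safety and efficacy of left subclavian artery (LSA) revascularization via in-situ laser-assisted fenestration during thoracic endovascular aortic repair", in type B dissection. The Design section describes a "single-arm, multicenter trial that planned to enroll 100 patients at 5 vascular centers". There is no control group, and every patient is meant to have both TEVAR and fenestration.

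The primary efficacy endpoint in Design is "freedom from all-cause death, LSA in-stent restenosis, and reintervention due to dissection progression, growth, and endoleak at 1 year after the procedure". It does not name technical failure of the fenestration, LSA occlusion or reintervention on the LSA stent.

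Methods describes the final imaging check, which includes the LSA stent: "arteriography was performed from the ascending aorta to assess the success of the procedure and to identify potential endoleak and residual stenosis of the LSA". Success is not defined there and enters no endpoint. Methods also describes how the hole in the aortic graft is lined: a "covered-stent (10% oversizing of the LSA in diameter) was deployed inside the fenestration".

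The SAP adds: "The patency rate of LSA and the all cause related mortality were estimated using the Kaplan-Meier method". It does not give patency the status of an endpoint, and it does not say how a patient without an LSA stent enters that estimate. It states no analysis, performance goal or component reporting for the efficacy composite. Unplanned reintervention appears in the SAP's wider list of adverse events, but that list serves the risk-factor regression and not the efficacy endpoint.

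**The concern.** The objective concerns a technique, whereas the main efficacy result describes a combined procedure in a sick population. Two problems follow.

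- **A poor result may have nothing to do with the LSA.** Patients have complicated or high-risk acute dissection. Death and reintervention for progression or growth can come from the disease or from TEVAR, and a single arm cannot separate these from the fenestration.
- **A good result may hide the most basic failure of the technique.** In-stent restenosis presupposes a stent. If the laser does not cross the graft, or no stent is delivered, the patient cannot have the one LSA-specific event. Occlusion counts only if it is read as restenosis, and the text does not say so.

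At stake is the sentence that the trial will support. Composite freedom at 1 year would naturally be reported as the efficacy of laser fenestration, although the figure does not require that a fenestration was achieved.

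**Working it through.** **Inputs.** From the documents: three components, 1 year, 100 patients, one arm. The documents give no expected rates and no basis for the sample size, so there is no planned figure to reproduce. Every rate below is an assumption.

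Notation, as 1-year probabilities: d = death, s = reintervention for progression, growth or endoleak, r = restenosis in a delivered stent, t = technical failure (no stent delivered).

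**Step 1. Can the composite look poor when the LSA stent does well?** Under independence, freedom = (1−d)(1−s)(1−r). Set r = 0:

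| d | s | Freedom with no restenosis |
|---|---|---|
| 2% | 2% | 0.98 × 0.98 = 96.0% |
| 5% | 5% | 0.95 × 0.95 = 90.2% |
| 8% | 8% | 0.92 × 0.92 = 84.6% |
| 10% | 15% | 0.90 × 0.85 = 76.5% |

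With d = s = r = 5%, freedom is 85.7%. The share of failures without restenosis is (1−r)[1−(1−d)(1−s)] / (1−freedom) = 0.95 × 0.0975 / 0.1426 = 65%. Over the four (d, s) pairs above and r from 3% to 10%, this share runs from 26% to 88%. So yes.

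**Step 2. Can it look good despite frequent restenosis?** Every restenosis is a composite failure, so freedom cannot exceed 1 minus the proportion of patients with restenosis. This needs no independence. Restenosis of 20% caps freedom at 80%, and 30% caps it at 70%. With d = s = 5%, freedom falls from 90.2% at r = 0 to 81.2% at 10%, 72.2% at 20% and 63.2% at 30%. So no.

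**Step 3. Can it look good despite technical failure?** Assume that patients with technical failure stay in the denominator and have the same d and s as the others.

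- Not counted, as the endpoint is worded: (1−d)(1−s)[1−r(1−t)]
- Counted as failure: (1−d)(1−s)(1−t)(1−r)
- Difference: (1−d)(1−s)t, which does not depend on r

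With d = s = r = 5%:

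| t | Not counted | Counted |
|---|---|---|
| 0% | 85.7% | 85.7% |
| 5% | 86.0% | 81.5% |
| 10% | 86.2% | 77.2% |
| 20% | 86.6% | 68.6% |

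As worded, the composite rises slightly as technical failure becomes more common. At t = 20% the difference is 0.9025 × 0.20 = 18.0 points. Over the (d, s) pairs of step 1 it runs from 0.765 × 0.20 = 15.3 to 0.9604 × 0.20 = 19.2 points. If such patients were instead left out of the analysis, the figure would be 85.7% whatever t is, so the failure would still not show.

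**The case against.** The strongest reply is that the composite fits the objective as written. The objective is revascularization during TEVAR for type B dissection. Whether perforating the graft harms the aortic repair is part of that question, so survival and aortic reintervention are within scope. This stands, and it is the reason to keep the composite.

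Two of the three components are also not purely aortic or disease outcomes. The endpoint restricts endoleak neither by type nor by site, so a leak at the fenestration that needs reintervention counts. Deaths caused by the combined procedure count too. This also stands, although a single arm cannot assign such events to their cause.

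A reader might infer that the composite can look good whatever happens to the fenestration. Step 2 rules that out for restenosis. It remains true only for failures that the endpoint does not name.

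A reader might also infer that the composite dilutes a rise in restenosis beyond detection. With d = s = 5%, a rise from 2% to 8% lowers freedom from 88.4% to 83.0%, so 5.4 of the 6.0 points pass through. The 95% Wilson intervals at n = 100 overlap (80.2–93.0% for 88/100, 74.5–89.1% for 83/100), but so do those for restenosis alone (0.6–7.0% for 2/100, 4.1–15.0% for 8/100). The overlap reflects the sample size and not the composite.

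Finally, the SAP does estimate LSA patency separately, so an LSA problem need not go unseen. That helps only in part: patency has no endpoint status, and the SAP does not say whether a patient who never received a stent is in the estimate.

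**Conclusion.** The point holds in a limited form. The efficacy composite is weakly specific to LSA revascularization, and its wording leaves out technical failure and reintervention on the LSA stent, and leaves occlusion open to interpretation. It is not uninformative about the technique, because restenosis is fully captured and endoleak reintervention may reflect the fenestration.

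The omission costs (1−d)(1−s)t. At 5% death and 5% reintervention, that is about 4.5 points of apparent efficacy at 5% technical failure, 9.0 at 10% and 18.0 at 20%. These figures rest on assumed rates, on independence of the components, and on technical failure leaving death and aortic reintervention unchanged. The bound in step 2 and the reading of the endpoint wording need none of these assumptions.

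The documents do not support replacing the composite as the basis of efficacy for the combined strategy. They do support a second endpoint, because without it the plan has no designated result that answers whether the LSA was revascularized and stayed open.

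**What to change.** 1. Keep the 1-year composite as the outcome of the TEVAR-plus-fenestration strategy, and report each component with its count and interval.
2. Name an LSA-specific key efficacy endpoint in all patients in whom fenestration was attempted. Success means a stent delivered through the fenestration with flow on completion arteriography, and an LSA that is patent at 1 year without restenosis, occlusion or LSA reintervention.
3. Count technical failures as failures from day 0. Treat death before 1 year without LSA failure as a competing event, so that LSA failure is estimated as a cumulative incidence. State how the SAP's Kaplan-Meier patency estimate relates to this endpoint and who is in it.
4. Base statements about the technique on the LSA endpoint and statements about the strategy on the composite.

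**Cost.** No added patients or procedures: completion arteriography and LSA patency are already part of the plan. The trial will report two efficacy figures, and the LSA figure may be the less favourable. The documents are written largely in the past tense, so if the endpoint is adopted after outcome data have been seen, it must be labelled post hoc.

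### Both primary rates pool emergent and delayed patients with no planned breakdown by timing, and, separately, the univariate screen can leave timing out of the risk-factor model

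*Combined protocol and SAP*

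**What the plan says.** The Design section describes a "single-arm, multicenter trial that planned to enroll 100 patients at 5 vascular centers". The population is taken as one cohort: the study "enrolled patients with complicated or high-risk acute TBAD".

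The Methods section then divides that cohort by presentation. Patients who did not respond to medical therapy, and those "presenting with rupture or impending rupture, malperfusion were treated emergently; otherwise, TEVAR procedures were performed 2 weeks later". How many patients fall in each group is not stated.

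Each primary endpoint is a single rate over everyone. "The primary safety endpoint was freedom from composite major adverse events", with six components, counted "within 30 days after the procedure". The efficacy endpoint is "freedom from all-cause death, LSA in-stent restenosis, and reintervention due to dissection progression, growth, and endoleak at 1 year after the procedure". Neither has an expected rate or a performance goal.

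The SAP summarises categorical variables as counts and proportions and plans no breakdown by timing or presentation. Its regression looks for risk factors of a wider, fourteen-item list of adverse events, and "only factors being found statistically significant in the univariate analysis were included in the multivariate analysis". Candidate factors are not named, no covariate is forced in, and the general significance threshold is P < 0.05.

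**The concern.** By the protocol's own rule, treatment timing marks how sick the patient was at presentation. That bears on two different analyses.

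**The primary rates.** The aim is to judge laser fenestration of the left subclavian artery. In a single-arm study the reader can only take the rate at face value or set it beside other experience. Either way, the reader needs to know what share of patients was emergent and how each group fared. The same technique, performing identically, would give a different pooled rate at centres receiving more emergent cases.

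**The risk-factor model.** Selection on univariate significance asks whether a variable reached P < 0.05 in this sample, not whether it is needed for adjustment. If timing misses the threshold by chance, any factor that is commoner in emergent patients can take up part of the effect of urgency and be reported as a risk factor in its own right.

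**Working it through.** **Inputs.** From the documents: N = 100, one arm, two timing groups, threshold P < 0.05 (taken as two-sided, since sidedness is not stated). Not in the documents, so assumed throughout: the emergent share *f*, the emergent event rate *pE* and the delayed event rate *pD*. The planned enrolment of 100 cannot be reproduced, because no target rate, margin, power or expected event rate accompanies it.

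**Step 1. How the pooled rate moves with case mix.** Pooled rate = *f* × *pE* + (1 − *f*) × *pD*. With *pE* = 20% and *pD* = 4%:

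- *f* = 20%: 0.2 × 20% + 0.8 × 4% = 4.0% + 3.2% = 7.2%
- *f* = 60%: 0.6 × 20% + 0.4 × 4% = 12.0% + 1.6% = 13.6%

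The difference is 6.4 points. For scale, the exact (Clopper-Pearson) 95% interval for 10 events in 100 is 4.9% to 17.6%, a half-width of (17.6 − 4.9)/2 ≈ 6.4 points. On these assumptions, case mix could move the rate by about as much as sampling error.

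**Step 2. How much of the pooled rate is excess emergent risk.** Share = *f* × (*pE* − *pD*) / pooled rate.

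| *pE* vs *pD* | *f* | Calculation | Share |
|---|---|---|---|
| 10% vs 5% | 10% | 0.5 / 5.5 | 9% |
| 20% vs 4% | 20% | 3.2 / 7.2 | 44% |
| 20% vs 4% | 60% | 9.6 / 13.6 | 71% |
| 30% vs 5% | 50% | 12.5 / 17.5 | 71% |

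The answer lies on either side of one half, depending on figures that the documents do not give.

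**Step 3. Chance that timing passes the univariate screen.** For each split of the 100 patients, every possible pair of event counts was enumerated with its binomial probability. The probabilities of the tables with P < 0.05 were then added up, under the logistic Wald test and the likelihood-ratio test. Ranges cover 30, 40 and 50 emergent patients and both tests.

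| Emergent vs delayed rate | Timing passes | Timing left out |
|---|---|---|
| 15% vs 5% | 24-43% | 57-76% |
| 20% vs 5% | 52-69% | 31-48% |
| 30% vs 5% | 86-95% | 5-14% |
| 40% vs 20% | 53-60% | 40-47% |
| 40% vs 15% | 76-82% | 18-24% |

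The last two rows are included because the screen runs on the fourteen-item outcome, whose event rates over the same period cannot be lower than those of the six-item primary composite.

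**Step 4. Do the two points connect?** They do not. The primary endpoints are crude proportions, and the regression is described only as a search for risk factors. Whether timing enters the model leaves both primary rates unchanged.

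**The case against.** The strongest reply is that pooling is not an error. The target population is defined as complicated or high-risk acute dissection, and the whole-cohort rate is an unbiased estimate for the patients enrolled. No comparison with an external series is planned, and nothing prevents the investigators from tabulating results by timing. All of this stands. It limits the first point to interpretation: the plan does not commit to the information needed to read the rate.

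A reader might go further and infer that the headline result mainly reflects case mix. The documents do not support that. They give neither the emergent share nor any event rate by timing, and step 2 shows a share anywhere from 9% to 71%. A reader might also infer that the screening rule distorts the primary rates. It cannot, for the reason in step 4.

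On the second point, a fair objection is that the fourteen-item outcome will yield more events than the primary composite, so a shortage of events is not established. That is right, and for a large contrast such as 30% vs 5% the screen is fairly reliable. But more events do not by themselves cure the weakness: at 40% vs 20% timing still fails four or more times in ten. It is also true that timing is not named as a candidate factor, so it may never be screened at all. That is a further reason to specify it in advance.

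**Conclusion.** The concern holds as two modest, separate points.

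1. The pooled primary rates are valid for the enrolled cohort, but they depend on an emergent share that the SAP does not undertake to report. The 7.2% to 13.6% range illustrates this under assumed rates and does not estimate what the trial will find. No comparable figure was worked out for the 1-year efficacy endpoint; the point applies there because that endpoint is also defined as one rate over the whole cohort.
2. The significance screen can omit timing even when its effect is real: roughly 3 to 5 times in 10 at 20% vs 5%, and 4 to 5 times in 10 at 40% vs 20%, but only about 1 time in 20 to 1 in 7 at 30% vs 5%. The consequence is confined to the risk-factor conclusions.

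Both rest on assumed event rates, and the second also on 30 to 50 of the 100 patients being emergent. The changes should be made, but the study's primary rates are not invalid without them.

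**What to change.** Amend the SAP in three respects.

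- Keep the whole-cohort rates as the primary results.
- Beside them, report both primary endpoints for emergent and delayed patients, giving the number in each group and exact 95% confidence intervals, labelled as descriptive. At 1 year, an exact binomial interval presumes that each patient's status is known.
- Include treatment timing in the multivariable adverse-event model whatever its univariate P value.

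Safety conclusions should not be confined to the two groups, because neither is large enough to carry them alone. For example, 8 events in 40 gives 9.1% to 35.6%, and 3 in 60 gives 1.0% to 13.9%. Those wide intervals are the main cost, together with one table and one model degree of freedom. No change to treatment, enrolment or visits is involved. The documents do not list the data collected, so it is an assumption that timing group can be derived from presentation and procedure date.

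### Screening risk factors of major adverse events by univariate P < 0.05 and refitting on the same patients pushes passing odds ratios away from 1 and lets null factors be named, yet the result is described as determined

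*Combined protocol and SAP*

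**What the plan says.** The Statistical Analysis Plan describes two steps. First, "Univariate logistics regression analysis was performed to determine the potential risk factors of major adverse events". Second, "only factors being found statistically significant in the univariate analysis were included in the multivariate analysis". The threshold follows at the end of the same paragraph: "Differences with a P value < 0.05 were considered statistically significant".

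The Design section of the Study Protocol gives the size of the study, which "planned to enroll 100 patients at 5 vascular centers", and states the outcome of the modelling more firmly than the SAP does: "Univariate and multivariate analyses determined the risk factors of composite major adverse events". The SAP's wording for the univariate step is softer, since it speaks only of potential factors.

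Neither section lists or counts the candidate factors, gives an expected number of events, limits the number of model terms, corrects for the screen, plans any shrinkage or validation, or labels the analysis exploratory.

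The modelled outcome is also not unique. The Design section defines the primary safety endpoint as "freedom from composite major adverse events (mortality, stroke, myocardial infarction, rupture, paraplegia, type Ia endoleak) within 30 days after the procedure", which has 6 components. The SAP sentence has 14, adding among others "major bleeding, acute kidney injury, limb ischemia, bowel ischemia, retrograde dissection", and gives no time window.

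**The concern.** A factor reaches the multivariate model only in samples where its estimated effect happened to be large relative to its standard error. Refitting the survivors on the same patients does not undo that selection, and the final p-values and confidence intervals are calculated as if no screen had taken place.

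Two different errors result, with different causes:

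1. **Exaggerated effects.** A real but modest factor that passes is on average reported too far from 1 (too high for a harmful factor, too low for a protective one). The drivers are the number of events, the true effect and the prevalence of the factor.
2. **Spurious factors.** Each null candidate gets its own chance to pass, so the probability of naming at least one rises with the number of candidates.

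At stake is what readers take from the trial about who is at risk: a chance finding may be published as a risk factor, or a modest factor as a strong one.

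**Working it through.** **Inputs from the documents:** 100 planned patients; univariate entry at P < 0.05; logistic regression. The plan states no figure for this analysis, so there is none to reproduce.

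**Assumed inputs (not in the documents):** two-sided Wald tests; 6, 10, 20 or 30 events; 15 binary candidates at 30% prevalence, independent of each other; one true factor with odds ratio (OR) 2. Variations are given below.

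**Step 1: the smallest OR that can pass.** For a binary factor of prevalence q and event proportion p among n patients, the standard error of the log OR is roughly 1/√[n·q(1−q)·p(1−p)]. To reach P < 0.05 the estimated OR must be at least about exp(1.96 × SE). With n = 100 and q = 0.3, n·q(1−q) = 21.

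| Events | 21·p(1−p) | SE | Approximate smallest passing OR |
|---|---|---|---|
| 6 | 1.184 | 0.919 | 6.1 |
| 10 | 1.890 | 0.727 | 4.2 |
| 20 | 3.360 | 0.546 | 2.9 |
| 30 | 4.410 | 0.476 | 2.5 |

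This is a large-sample approximation, and the cut-off varies from sample to sample. It still shows the mechanism: if the true OR is 2, an estimate near the truth will generally not pass. The candidate count does not appear in the formula.

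**Step 2: simulation of the SAP rule** (univariate screen, then maximum-likelihood refit; 3,000 to 4,008 trials per scenario).

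| Mean events | 6 | 10 | 20 | 30 |
|---|---|---|---|---|
| True factor (OR 2) enters the model | 9% | 17% | 27% | 33% |
| Its median OR when it enters | 7.2 | 5.2 | 3.7 | 3.3 |
| Median divided by 2 | 3.6 | 2.6 | 1.85 | 1.65 |
| Final model names at least one null factor | 19% | 28% | 39% | 43% |

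The 6-event median is unstable (7.2 to 8.5 over separate runs), because few trials contribute. A separate calculation at 40% prevalence found estimates close to the truth without selection (true OR 2: 2.06 at 10 events, 2.03 at 20). After the screen it gave geometric means of 6.5 and 3.9.

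**Step 3: which input drives which harm.** With 1/5/15/30 candidates, the median OR on entry was 3.66/3.57/3.69/3.72 at 20 events and 3.20/3.29/3.29/3.26 at 30. Candidate count therefore leaves the exaggeration unchanged. It does drive spurious naming: 5/10/14/15% with 5 candidates and 23/35/49/54% with 20, at 6/10/20/30 events. For k independent null candidates tested at an exact 5% level, the chance that at least one passes is 1 − 0.95^k: 23% for k = 5, 54% for 15, 64% for 20. The simulated values are lower mainly because the Wald test is conservative when events are few.

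**Step 4: sensitivity.**
- Correlated candidates (latent correlation 0.3): null factor named in 14/25/34/37%; median OR on entry 6.6/4.4/3.2/3.0.
- Independent continuous candidates, true OR 1.37 per SD: null factor named in 40/44/46/45%; median OR on entry 3.1/2.4/1.9/1.8.
- True OR 3: median on entry 8.1/5.8/4.2/3.8, so only 1.3 to 1.4 times too large at 20 to 30 events.
- Correlated continuous factor, true OR 2 per SD: no exaggeration at 20 to 30 events.

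**Step 5: the alternative.** One, one, two and three pre-specified terms at 6/10/20/30 events were fitted by Firth's method and reported whatever their p-values. If the true factor (OR 2) is on the list, the median OR is 2.1/2.0/2.0/2.0 and the profile-likelihood intervals cover in 95-97% of trials. Looking only at trials where the term is significant, the median is 6.9/4.7/3.6/3.2, much as under the SAP rule. When no candidate is real, a null factor is named in 3/4/10/14% of trials, against 19/28/41/46% under the SAP rule. Much of that gap reflects fewer tests.

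**The case against.** The strongest reply is that this is a secondary analysis done in a common way, that the SAP itself speaks of potential factors, and that every magnitude above rests on assumed inputs. All of that is true. The assumed results run from 5% to 54% for spurious naming among binary candidates alone, and the plan does not show where in that range the trial lies. What the reply does not remove is the direction of the error, the intervals that ignore the screen, or the Design section's firmer verb.

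The alternative also offers little extra power: 13/19/26/32% against 8/16/25/30% for a true OR of 2. Selecting its significant results brings the exaggeration back. This stands, and it shows where the benefit lies: in pre-specification, full reporting and labelling.

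Stronger readings are tempting and should be resisted:

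- A reader might infer that a long candidate list inflates the odds ratios. Step 3 shows that it does not; it adds spurious factors.
- A reader might infer that every passing odds ratio is too large. For protective factors the error lies in the other direction, and for strong factors with many events it is small or absent.
- A reader might infer that the safety or efficacy conclusions are affected. Neither primary endpoint is estimated from this model, and no treatment comparison rests on it in this single-arm study.
- A reader might rule out emergent versus delayed procedure as a covariate, because patients "presenting with rupture or impending rupture, malperfusion were treated emergently" and rupture is also a component of the outcome. For the Design section's composite this does not follow, since only events after the procedure count. The SAP's undated list leaves the overlap open.

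**Conclusion.** The concern holds for the risk-factor analysis. The entry rule and the description of its result as determined are both in the documents, and together they present selected estimates as established findings. Under the base assumptions, a true OR of 2 is missed in most trials. When it does enter, it typically reads about 7-8, 5.2, 3.7 or 3.3 at 6, 10, 20 or 30 events, and a null factor is named in about 19/28/39/43% of trials. These figures illustrate the problem and do not predict this trial's results, because event count, candidate count, prevalence and effect size are all absent from the plan. The point should be corrected, but its consequence is limited to the risk-factor claims. The mismatch between 6 and 14 components is a separate matter and adds no weight here, except that the modelled outcome has to be named before its events can be counted.

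**What to change.** Delete the univariate-significance entry rule. The text is largely in the past tense, so the remedy depends on whether outcomes have been seen.

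**If outcomes have not been seen:** pre-specify a short ranked list of baseline factors, chosen on clinical grounds and not defined by a component of the modelled outcome. Limit the number of terms in relation to observed events, for example about one per 10 events with at least one. Fit the listed terms whatever their univariate p-values, and report every estimate with its 95% confidence interval. Firth's penalised likelihood is a sensible safeguard against non-finite estimates: at 6 events the true binary factor had no finite univariate estimate in about 9% of simulated trials. Report all other univariate results in full, as exploratory.

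**If outcomes have been seen:** label the whole analysis exploratory and report all candidates examined, including those that did not pass.

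**In either case:** change the Design section's verb from determined to explored, and state which composite and time window is modelled, reconciling the Design section with the SAP. Emergent versus delayed procedure may be on the list if only events arising after the procedure are counted.

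**Cost:** SAP wording and one penalised-likelihood routine; no new data. Few factors can be reported, with little or no adjustment when events are few, and factors off the list are only described. Power stays low even for a correctly listed factor (27/38/57/67% for a true OR of 3 at 6/10/20/30 events), so a non-significant result says little.
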